5.3 Additional / Exploratory analyses

No additional or exploratory analyses are planned. Details of exploratory analyses which would have been performed had the trial continued to full enrolment are described in the Appendix.

5.4 Missing data

The availability of outcome data will be summarised as described in section 4.1.3. Given the small sample size we do not plan any imputation of missing data (except where part of questionnaire scoring). Methods which would have been employed had the trial continued are described in the Appendix.

6. SAFETY

6.1 Adverse Events

Safety data will be reported in the Safety Analysis Set, with adverse events reported according to treatment received at the time of AE onset.

The following metrics will be used to provide an overall summary of adverse events reported while exposed to each treatment group, see Example Table 10:

- The number of participants exposed to each treatment group.
- The total exposure time (measured in years) to each treatment group, i.e. a sum across all participants of the amount of time they were exposed to each treatment group.
- Number and proportion of participants affected by at least one adverse event while exposed to each treatment group. Percentages will be calculated out of those exposed.
- Worst grade (mild, moderate, severe) adverse event reported while exposed to each treatment group. This will be tabulated with percentages calculated out of those exposed.
- Total number of adverse event occurrences reported by each participant while exposed to each treatment group. This will be tabulated (with percentages calculated out of those exposed) and/or reported as median and range, as appropriate
- Total number of unique adverse event occurrences (i.e. different preferred terms) reported by each participant while exposed to each treatment group. This will be tabulated (with percentages calculated out of those exposed) and/or reported as median and range, as appropriate
- Total number of adverse event occurrences reported across all participants while exposed to each treatment group. This will also be broken down by severity (mild, moderate, severe).
- The incidence rate (IR) of adverse event occurrence while exposed to each treatment group (i.e. total number of AE occurrences / total exposure time).

For each adverse event, at the preferred term level, we will also report the following metrics by treatment group, see Example Table 11:

- The number and proportion of participants experiencing the adverse event at any point while exposed to each treatment group. Percentages will be calculated out of those exposed.
- The worst reported severity (mild, moderate, severe) for the adverse event at any point while exposed to each treatment group. Percentages will be calculated out of those exposed.
- The total number of occurrences of the adverse event while exposed to each treatment group.
- The total number of occurrences of the adverse event, by severity (mild, moderate, severe), while exposed to each treatment group.

This data may also be presented graphically as dot plots of the proportion of participants affected by each adverse event. The number of participants affected and the total number of occurrences will be shown on the graph. See Example Figure 5. Had the trial continued to full enrolment the graph would have also shown a measure of relative risk with 95% CIs, with separate graphs produced for the comparison of fludrocortisone and control, midodrine and control, and fludrocortisone and midodrine. If there are many different adverse events reported we will focus on the graphical presentation of only those occurring in a specified proportion of participants (e.g. >3% participants in either group).

The same summaries will also be reported for adverse reactions (adverse events reported as possibly, probably or definitely related to trial treatment) and for non-serious events (as required for EudraCT reporting).

Adverse events which resulted in treatment discontinuation will also be tabulated. Percentages will be calculated out of those exposed to each treatment group.

Example Table 10: Summary of adverse events

	Control	Fludrocortisone	Midodrine
Number of participants exposed; N			
Total exposure time (years); N			
Number of AEs per			
participant; N (%)			
0			
1-3			
4-6			
>6			
Median (IQR); Range			
Number of unique AEs per			
participant; N (%)			
0			
1-3			
4-6			
>6			
Median (IQR); Range			
Worst grade reported across all AEs; N (%)			
Mild			
Moderate			
Severe			
Total number of AEs			
reported; N			
Mild			
Moderate			
Severe			
Incidence of AEs; IR (95% CI)			

		Number	(%) of participants	affected ^{1,2}	Number of occurrences ¹			
Adverse event term		Control	Fludrocortisone	Midodrine	Control	Fludrocortisone	Midodrine	
		N =	N =	N =	N =	N =	N =	
	Overall							
Nausaa	Mild							
Nausea	Moderate							
	Severe							
	Overall							
Usadasha	Mild							
Headache	Moderate							
	Severe							
	Overall							
AE 1	Mild							
AEI	Moderate							
	Severe							
	Overall							
AE 2	Mild							
AE Z	Moderate							
	Severe							

Example Table 11: Summary of adverse events by type

¹While exposed to each treatment group

 2 % calculated out of total number exposed. If >1 occurrence per participant the worst reported severity is tabulated

Example Figure 5: Proportion of participants affected by each AE

6.2 Serious Adverse Events

A chronological listing of reportable serious adverse events (SAEs) will be presented, see Example Table 12.

The following metrics will also be reported:

- The number and proportion of participants reporting at least one SAE while exposed to each treatment group. Percentages will be calculated out of those exposed.
- The total number of occurrences of SAEs, across all participants, while exposed to each treatment group.
- For each SAE (using the preferred term), the total number of participants affected and the total number of occurrences while exposed to each treatment group.

Example Table 12: Line listing of all SAEs

	SAE	Rand.	IMP at	IMP start +		SAE onset			Serious		Outcome
ID	no.	group	onset	end dates	Description	date	Severity ¹	Causality ²	criteria ³	Outcome ⁴	date

¹*Mild; moderate; severe*

²*Related; unrelated; unable to determine*

³Resulted in death; Life threatening; Inpatient hospitalisation / prolonged hospitalisation; Persistent or significant disability/incapacity; Congenital anomaly / birth defect; Important medical event

⁴*Recovered; Condition improved; Condition deteriorated; Condition unchanged; Participant died; Recovered with sequelae; Condition stable and no change anticipated*

Non-reportable serious adverse events will also be summarised.

6.3 Other safety measures

We do not plan analyses of any other safety measures (e.g. laboratory values, vital signs etc.).

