5.4.2 Follow-up Visits (Three, six and 12 Months)

The clinical/ research team will schedule the three-, six- and 12-month follow-up clinic appointments with all participants. These should be face-to-face, if possible; however, remote follow-up visits are acceptable. This is a pragmatic study so some variability in the timing of follow-up assessments is acceptable (see schedule of Events for follow-up windows).

All participants will have their supine and nadir standing BP taken or provide self-recorded BP measurements if follow-up is remote (acceptable methods for obtaining BP measurements are listed in Section 5.5.1).

Blood tests will be carried out/arranged as part of their usual clinical care (see Schedule of Events).

At the three-month follow-up participants who were randomised to receive IMP will be asked to confirm that they have started the prescribed IMP.

Participants will be asked to either provide their falls diary at each follow-up visit or provide details from their falls diary over the phone when they speak to the site research team member or clinician. At each consultation, participants will be reminded to complete their falls diary and bring it with them to their next face-to-face follow-up visit or have it to hand to allow the information to be provided over the phone/video call. If participants forget to bring their falls diaries to their face-to-face consultation or are unable to attend face-to-face consultations this data can be collected over the phone and a new diary can be posted out with a self-addressed envelope for return of the partially completed diary to enable timely data collection.

Participants will be required to complete the OHQ, EQ-5D-5L, Nottingham Extended ADL Scale and the Health and Social Service Use questionnaire. Additionally, participants will complete a Time and Travel Questionnaire at the six-month follow-up consultation. For remote visits, these questionnaires will be completed by the clinician over the phone/videoconference with the participant.

Data regarding adherence to trial intervention, culprit medications and Adverse Events will be collected and recorded in the CRF.

For sites who carry out face-to-face follow-up with patients in the community as routine practice, these consultations can be scheduled at the participant's home. However, a medically qualified, GMC registered clinician must retain oversight.

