5.6.1 Supine Hypertension

The decision to discontinue study medication because of supine hypertension lies with the site PI. No threshold for discontinuation is stipulated, as the balance of risk and benefit will differ from participant to participant, but a supine systolic BP of <160 should not usually lead to discontinuation of medication [31]. A diagnosis of supine hypertension should not be based on a supine BP measured within four to six hours of a midodrine dose.

Although supine hypertension may increase the risk of cardiovascular events, some individuals may be willing to accept the risk if their symptoms of OH outweigh the risk. This is particularly true for those who have profound drops in BP, where a higher supine BP may be required to achieve higher standing BPs.

Home monitoring, ideally with an automated 24 hour BP monitor, is best practice if feasible. Dose reduction of fludrocortisone or midodrine may improve supine hypertension. An alternative strategy is the encouragement of head-up posture during recumbency, by elevating the head of the bed.

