Participants will be classed as fallers if they report at least one fall over the 12 month period and a non-faller if they did not report a fall and returned at least one fall diary; i.e. participants who do not return at least one fall diary will be excluded from the analysis. We will also categorise participants as a single faller if they fall once, a recurrent faller if they fall twice or more, and a non-faller if they do not report any falls.

The number of faints (syncopal events) for each participant will be summed over the 12 month period. The syncopal event rate will be calculated as described above. In addition, we will report the total number, and rate of, a combined outcome of fall and faints.

Time to first fall will be measured as the time from randomisation to the first reported fall.

Fall related injuries are reported as free-text fields. There will be a medical review of any coding of free-text fields required.

Standing blood pressure and postural blood pressure drop

The lowest (nadir) standing blood pressure (systolic and diastolic) is measured at baseline, three, six and 12 month follow-up.

Blood pressure will also be measured in the supine position (lying down) at baseline, three, six and 12 month follow-up.

Postural blood pressure drop will be defined as (supine – lowest standing blood pressure) for systolic and diastolic measurements at each time point.

For each measurement the change from baseline will also be calculated as the follow-up value minus the baseline value.

Hospital admissions

Hospital admissions during the 12 month trial period will be collected from medical records. The number of admissions per participant will be calculated.

Reasons for admission will be tabulated. 'Other' reasons will be coded/grouped where possible with a medical review of any coding.

The rate of hospital admissions per person year will be calculated in each arm as the total number of admissions from all participants in that arm divided by the total observation time for all participants in that arm. For each participant their observation time will be measured as the time (in years) from randomisation to their last completed follow-up visit.

Side effects and the safety data associated with each treatment strategy

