Adverse Events (AEs) will be collected over the 12-month trial period. At each follow-up visit participants will be asked about any side effects or adverse events they have experienced. This will be by open-ended questioning rather than a review of specific side effects or symptoms. Adverse events will be coded using the MedDRA dictionary (version 24) and summarised at the preferred term level. Severity (mild / moderate / severe),

seriousness (Yes / No) and relationship to study treatment (Unrelated / Unlikely to be related / Possibly related / Probably related / Definitely related) will also be collected.

An adverse event of the same type (i.e. same preferred term) will be counted as a separate occurrence if the start and end date of sequential events are separated by > 1 day.

Further detail on how adverse events will be summarised and reported is provided in section 6.

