Fall-related injuries will be tabulated by type, with the number of participants affected and the total number of occurrences reported by randomised treatment group. The number and proportion of participants reporting at least one fall-related injury will be tabulated by treatment group. The total number of fall-related injuries reported per participant will be tabulated as frequency and percentage and as mean, SD, median and range. The total number of fall-related injuries reported in participants allocated to each treatment group will be presented. For the purpose of calculating percentages the number of participants returning at least one fall diary will be used as the denominator.

Example Table 8: Falls and syncopal events

	Control	Fludrocortisone	Midodrine
	N =	N =	N =
Number of falls			
0			
1			
>2			
Mean (SD)			
Median (Range)			
Fall rate			
Total number of falls			
Total follow-up time (years)			
Incidence rate (95% CI)			
Fallers / non-fallers			
≥1 fall / N (%)			
Time to first fall			
< 3months			
3-6 months			
>6 months			
Number of syncopal events			
0			
1			
>2			
Mean (SD)			
Median (Range)			
Syncopal event rate			
Total number of syncopal events			
Incidence rate (95% CI)			
Number of falls and syncopal events			
0			
1			
>2			
Mean (SD)			
Median (Range)			
Falls and syncope event rate			
Total number of events			
Incidence rate (95% CI)			

Standing blood pressure and postural blood pressure drop

The methods described below will be applied to the following variables; nadir standing systolic blood pressure (BP), nadir standing diastolic BP, systolic postural BP drop, diastolic postural BP drop.

Analysis Set 1 will be used for analysis. All data available will be reported according to randomised treatment allocation.

Each BP measurement and change from baseline will be summarised descriptively by randomised treatment group. The number with data, mean, standard deviation, median and range will be summarised at each visit.

Example Table 9: Blood pressure

Diago processo	V	/alue at follow-up vi	isit	Change from baseline			
Blood pressure	Control	Fludrocortisone	Midodrine	Control	Fludrocortisone	Midodrine	
Nadir standing							
Month 3*							
N							
Systolic							
Mean (SD)							
Median (Range)							
Diastolic							
Mean (SD)							
Median (Range)							
Postural drop							
Month 3*							
N							
Systolic							
Mean (SD)							
Median (Range)							
Diastolic							
Mean (SD)							
Median (Range)							

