Appendix Figure 2: Number of falls (note this is not genuine data)

Standing blood pressure and postural blood pressure drop

The analysis methods described below would be applied to the following variables; nadir standing systolic blood pressure (BP), nadir standing diastolic BP, systolic postural BP drop, diastolic postural BP drop.

Analysis Set 1 would be used for analysis. All participants with data available would be analysed according to their randomised treatment allocation.

Each BP measurement would be summarised descriptively by randomised group. The number with data, mean, standard deviation and the median, IQR and range would be summarised at each visit. Data may have also been presented graphically by randomised treatment group as the mean value with 95% CIs at each visit.

As for the OHQ data, a linear mixed-effects model would have been fitted to the three, six and 12 month data. Fixed effects would include baseline BP measurement, baseline age (<80 years or >=80), aetiology (neurogenic or non-neurogenic) and a treatment assignment x time interaction term. Random effects would include site and individual (nested within site). This model would be fitted using REML and an unstructured covariance matrix.

Missing responses would be assumed to be missing at random (MAR). Participants would be included in the model if they had at least one BP measurement available from the three, six or 12 month follow-up visit.

From this model we would obtain the estimated mean difference in the three, six and 12-month follow-up BP measurements between fludrocortisone and control and between midodrine and control. This would be reported with a corresponding 95% confidence interval, see Appendix Table 4.

Assumptions of the model would be investigated as described for the analysis of the primary outcome.

	Control	Control Fludrocortisone Midodrine	Midodrine	Mean difference (MD)	
				Fludrocortisone -	Midodrine -
Blood pressure				control	control
	N; Mean (SD)	N; Mean (SD)	N; Mean (SD)	MD (95% Cl) ;	MD (95% CI) ;
	it, mean (52)	N, Mean (5D)	it, incan (52)	p-value	p-value
Nadir standing					
Month 3					
Systolic					
Diastolic					
Month 6					
Systolic					
Diastolic					
Month 12					
Systolic					
Diastolic					
Postural drop					
Month 3					
Systolic					
Diastolic					
Month 6					
Systolic					
Diastolic					
Month 12					
Systolic					
Diastolic					

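### Supine blood pressure is measured at every visit but never summarised, so raised supine readings are reported only if a site records them as adverse events

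*SAP*

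**What the plan says.** **Collection.** Protocol 5.4.2 states: "All participants will have their supine and nadir standing BP taken or provide self-recorded BP measurements if follow-up is remote". SAP 2.4.2 agrees: "Blood pressure will also be measured in the supine position (lying down) at baseline, three, six and 12 month follow-up". The schedule of events (Protocol 5.5) also lists supine and standing pressure at baseline and at every follow-up visit.

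**Use.** The SAP gives supine pressure one role, as a component of another variable: "Postural blood pressure drop will be defined as (supine – lowest standing blood pressure"). SAP 5.2 then lists the variables to be summarised: "nadir standing systolic blood pressure (BP), nadir standing diastolic BP, systolic postural BP drop, diastolic postural BP drop". The SAP Appendix, which describes what would have been done at full enrolment, names the same four. Early closure is therefore not the cause of the omission.

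**Safety.** SAP 6.3 reads "We do not plan analyses of any other safety measures (e.g. laboratory values, vital signs etc".). On adverse events, SAP 2.4.2 says of the questions put to participants at follow-up visits: "This will be by open-ended questioning rather than a review of specific side effects or symptoms".

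**Standing of supine hypertension in the protocol.** It is an exclusion criterion at baseline where risk outweighs benefit (4.3). It has its own section on stopping study medication (5.6.1), which notes that "supine hypertension may increase the risk of cardiovascular events", leaves the decision to the site PI and sets no threshold. Side effects and safety are a stated secondary objective (Protocol 2.2, SAP 1.2.2).

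**The concern.** Both drugs are given to raise standing pressure, and Protocol 5.6.1 recognises that supine pressure may rise too and says that reducing the dose of either drug may improve it. The planned table shows the intended effect, standing pressure, and the gap between postures. It does not show the supine level itself. A raised supine reading is a measurement and need not be a symptom, so a participant who feels well has no reason to mention it when asked an open question.

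At stake is how well the report answers the safety objective for a harm that the protocol singles out, when the readings are already in the database. Numbers will be small and the report descriptive. Its data are meant to inform later work (SAP 5.1.1 mentions future meta-analyses and sample size calculations), and a later user would want the supine values.

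**Working it through.** The plan states no figure to reproduce. The check has two parts.

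**1. Where could a raised supine reading appear in the report?**

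| Route | What the documents provide | Does it show supine pressure? |
|---|---|---|
| Secondary outcome tables (SAP 5.2, Example Table 9) | Nadir standing and postural drop, systolic and diastolic | Not directly |
| Appendix models | Same four variables | No |
| Other safety measures (SAP 6.3) | No vital-sign analysis | No |
| AE tables (SAP 6.1) | Preferred term, worst severity, by treatment at onset | Only if recorded as an AE |
| AEs leading to stopping treatment (SAP 6.1) | Tabulated | Only if recorded and treatment stopped |
| SAEs (SAP 6.2) | Listed and counted | Only if serious |
| Discontinuation reasons (Example Tables 3 and 4) | Lack of efficacy, side effects, other | Not separately identified |

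The AE route is open, because hypertension is not on the list of events exempt from recording (Protocol 7.2, 7.3). It has weaknesses:
- No blood pressure value triggers recording.
- Questioning is open-ended.
- Severity is graded by discomfort and interference with daily activity (Protocol 7.4.1), so a symptomless reading would tend to grade as mild whatever its level.

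**2. What can be recovered from Example Table 9?**

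By the SAP's definition, supine = standing + drop for each participant. On the same participants:

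- mean(supine) = mean(standing) + mean(drop)
- SD(supine)² = SD(standing)² + SD(drop)² + 2 × r × SD(standing) × SD(drop)

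The mean is recoverable, approximately, because the table gives a separate N for each block and the participants may differ. The SD is not, because the correlation r between standing pressure and drop is not reported. The range and any count above a cut-off are not recoverable either.

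*Mean, illustrated.* Suppose a drug raises supine and standing systolic pressure by 15 mmHg each (assumed). Example Table 9 shows standing +15 and change in drop 15 − 15 = 0. Adding the two gives supine +15.

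*Counts, illustrated.* The values below are assumptions, none taken from the documents: normal distribution, mean supine systolic 150, standing SD 20, drop SD 15. The cut-point of 160 mmHg appears in Protocol 5.6.1 but is not set there as a threshold; it serves only for illustration.

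- r = −0.8: SD = √(400 + 225 − 480) = √145 = 12.0; share at or above 160 = 1 − Φ(10/12.0) = 20.3%
- r = 0: SD = √625 = 25.0; share = 1 − Φ(10/25.0) = 34.5%
- r = 0.5: SD = √(400 + 225 + 300) = √925 = 30.4; share = 1 − Φ(10/30.4) = 37.1%

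The same published means and SDs thus fit a share anywhere from about 20% to 37%. Widening the assumptions (mean 140 to 150, SD pairs 20/15 and 25/20, r from −0.8 to 0.5) takes it from 4.8% to 39.9%.

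**The case against.** The strongest reply is that the SAP does what the protocol asks. The blood pressure objective is standing pressure and postural drop (Protocol 2.2), and supine pressure is never named as an outcome. That stands: no protocol outcome has been dropped, and the point is a gap in safety reporting, not a contradiction between the documents.

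Second, a reader might infer that supine hypertension will go unreported. The documents do not support this. It is not exempt from AE recording, and if recorded it would appear by preferred term and treatment received, among adverse reactions if judged related, and among events leading to discontinuation or SAEs where applicable. Site staff also see the supine reading at follow-up, and the PI decides on stopping drug, so a clinically important value is likely to be noticed. What remains is that capture rests on unstandardised recording.

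Third, a reader might rank supine hypertension as the leading harm. The protocol ranks none. Its rationale (1.2) mentions possible excess hospitalisation with fludrocortisone and side effects in more than 1 in 10 with midodrine.

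Fourth, a reader might say that Example Table 9 shows only the favourable side of a pressor effect. Since the mean can be reconstructed, that goes too far. The spread and the counts are what is lost.

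Fifth, counts of high readings could mislead. Protocol 5.6.1 warns against diagnosing supine hypertension from a reading taken in the four to six hours after midodrine, and neither document describes recording the interval. Readings may come from records up to six weeks old or from home measurement (Protocol 5.4.1). This stands. It calls for a clear caveat and for a summary by treatment received, but it is not a reason to leave out the values.

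Last, the trial closed early, is descriptive only, and may share individual data later (Protocol 12.11, 13.5). This lowers the stakes but does not replace a few rows in the main report.

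**Conclusion.** The concern holds in a limited form. Supine pressure is measured in all arms at every visit, enters the analysis only through postural drop, and is absent from the blood pressure summaries in both the current plan and the Appendix. Raised supine readings would reach the report only through AE recording that has no pressure definition.

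The loss is specific. Group means are roughly recoverable, while the SD, range and number of participants with high readings are not. How far this would distort the picture cannot be quantified from the documents. The 20% to 37% span rests wholly on assumed values and shows only that the planned tables do not determine the count.

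The 160 mmHg figure should not be read as a protocol threshold, since Protocol 5.6.1 declines to set one. Whether baseline supine pressure is shown in Example Table 2 cannot be judged, because its row labels are not legible in the text available. In a small descriptive report this is a worthwhile, low-cost improvement to the answer on safety. It does not affect the primary outcome.

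**What to change.** 1. **Example Table 9.** Add supine systolic and diastolic pressure by visit and randomised group: N, mean, SD, median, range and change from baseline. Extend the variable list in SAP 5.2 to match.
2. **SAP 6.3.** Replace the blanket exclusion with a descriptive safety summary of supine pressure by treatment received at the visit, in keeping with the Safety Analysis Set (SAP 3.4). Treatment changes are already recorded in the eCRF (Protocol 6.9.1). Include the number and percentage of participants above a cut-off that the trial team writes into the SAP before supine values are tabulated by arm. Label it a descriptive cut-off, not a clinical threshold.
3. **Footnote.** State the Protocol 5.6.1 caution about readings soon after midodrine, that neither document describes recording the time from dose to reading, and that readings may come from medical records or home measurement.

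No testing and no new data are needed. The cost is a short SAP amendment and a few table rows. The drawback is that the counts need cautious reading, above all for midodrine, and will rest on few participants.
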